4.1. Primary Endpoint

4.1.1. The primary outcome will be safety and tolerability will be determined by type, frequency and duration of adverse events (AE) and serious adverse events (SAE) in subjects receiving valganciclovir versus placebo.

4.2. **Secondary Endpoints:** We will evaluate for trends in other clinical endpoints, as well as viral and immune endpoints over time in the valganciclovir group compared to the placebo group.

4.2.1. We will determine the change in pulmonary function tests including forced vital capacity (FVC) and diffusing capacity for carbon monoxide (DLCO) in the valganciclovir treated group compared to placebo during active treatment and post-treatment follow-up. PFTs will be measured at baseline, 3 months (12 weeks), 6, 9 and 12 months after randomization to determine the FVC slope (change in FVC over time) and change in diffusion capacity (DLCO).

4.2.2. We will determine the effect of valganciclovir therapy on viral load in cell-free BAL fluid.

4.2.2.1. We will evaluate the change from baseline in daytime oxygen requirements. Oxygen requirements will be measured at study visits baseline, 3, 6, 9, 12 months. At each study visit, while at rest, the subject will be placed on the amount of supplemental O₂ required at the enrollment visit. After 5 minutes, the SpO₂ on this supplemental flow rate will then be recorded and evaluated in comparison to baseline. In addition, the patient will have his/her supplemental oxygen requirement determined to maintain oxygen saturation $\geq 88\%$ at rest. The change in liters per minute flow rate in oxygen compared to baseline will be recorded.

4.2.3. Exercise capacity will be determined on the basis of the 6 minute walk test (6MWT). The principal exercise capacity measurement will be the change in distance until SpO₂ reaches 80% compared to baseline. 6 MWT will be measured at study visits baseline, 3, 6, 9, 12 months. The 6MWT will be performed using a standardized protocol while the subject is breathing room air (i.e. without supplemental oxygen).

4.2.4. Additional secondary endpoints will analyze the immune response to herpesviruses by analyzing PD-1 expression by T lymphocytes and quantifying CMV- and EBV-antigen specific CD8⁺ T cell immune responses.

5. Background and Significance

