Randomization will be to pirfenidone plus placebo or pirfenidone plus valganciclovir. We prefer to have all subjects on pirfenidone as the standard of care for this study since the majority of patients elect to be treated with pirfenidone in our clinic. In addition, we anticipate valganciclovir will be better tolerated in combination with pirfenidone. We propose to enroll and randomize all eligible subjects with evidence of current or past EBV or CMV infection as determined by serologic testing for anti-EBV and CMV antibodies (total n=30) to treatment with pirfenidone plus valganciclovir (20 patients) or pirfenidone plus placebo (10 patients) for 12 weeks (**Fig. 1**). In order to maximize exposure to active treatment and assess for safety and tolerability, randomization will be 2:1 valganciclovir vs. placebo. The primary outcome will be safety and tolerability will be determined by type, frequency and duration of AE and SAEs. All study subjects will be offered bronchoscopy with BAL at study initiation and upon completion of treatment (12 weeks). Subjects will then be followed up at routine clinic visits at 6, 9 and 12 months for data collection.

[figure not shown]

Figure 1. Study flow chart.

6.2 **Rationale for Blinding and Placebo:**

6.1.1. A RCT is necessary given the clinical heterogeneity of IPF, and the inability to have two similar arms without randomization. A placebo arm will minimize bias since GI upset is a side effect of valganciclovir and standard treatment, pirfenidone. All subjects will be provided standard of care treatment to be applied equally across study groups as much as feasible and blinding will help avoid bias in the care provided.

6.1.2. Blinding is necessary to have optimal scientific validity, to make objective assessments of treatment effects, and to minimize dropout rates across study arms. In this study, there is particular concern that without blinding, subjects may opt to obtain off-label anti-viral therapy from non-study physicians if they become aware of the presence of herpesviruses in their lungs.

7. **Study population:** The study population will consist of male and female patients diagnosed with IPF, ages 21 and above, who are followed in the outpatient clinic setting.

7.1. **Inclusion criteria** will be:

- 7.1.1. age ≥ 21 and ≤ 80 years
- 7.1.2. ability to provided informed consent
- 7.1.3. diagnosis of probable or definite IPF according to ATS criteria(11)

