- 12.1. Contraindications, precautions, and side effects of study medications: Valganciclovir is FDA approved for the treatment and chronic suppression of herpesviruses, and has a good safety profile post marketing. The dose of valganciclovir recommended for this study is well within the FDA approved dosing range for other indications. The major side effect of valganciclovir is bone marrow suppression causing anemia, leukopenia, or thrombocytopenia. GI upset (nausea and diarrhea) is another reported side effect. These side effects will be monitored by routine laboratory testing and monitoring of subject diaries and direct questioning. Dose adjustments of valganciclovir are required for renal impairment, and dose modifications for renal insufficiency will be made according to recommended guidelines based on estimated creatinine clearance using the Cockcroft-Gault equation. For both valganciclovir and pirfenidone, there are no known major drug interactions requiring special clinical monitoring.
- 12.2. Valganciclovir safety and handling. In animal studies ganciclovir was found to be mutagenic, teratogenic, aspermatogenic and carcinogenic. Valganciclovir is considered a potential teratogen and carcinogen in humans with the potential to cause birth defects and cancers, and may cause temporary or permanent inhibition of spermatogenesis. Women of childbearing age will be required to use a medically approved means of contraception and will have urine pregnancy tests performed with each study visit. Male patients will be advised to practice barrier contraception during and for at least 90 days following treatment with valganciclovir. Tablets will not be broken or crushed. Since valganciclovir is considered a potential teratogen and carcinogen in humans, caution will be observed in handling broken tablets. Direct contact of broken or crushed tablets with skin or mucous membranes will be avoided. If such contact occurs, thorough washing with soap and water, and washing of eyes with sterile water will be performed. Unused medication will be returned to the pharmacy for disposal.

13. Data Management and Statistical Analysis Plan

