13.2. Sample Size and Randomization

- 13.2.1. Power analysis: This pilot study is designed to determine tolerability and safety of valganciclovir as add-on therapy to pirfenidone. Pirfenidone is reported to be discontinued in 13% of subjects due to adverse events, almost all of which occur within the first 4 weeks of treatment (based on AE profiles from the ASCEND study). Therefore, we do not expect any

placebo treated subjects to withdraw from this study. Using a 2:1 randomization (valganciclovir:placebo) and enrolling 30 subjects will allow us to detect an increased withdrawal rate in the valganciclovir group in the range of 25% (75% power with a one-sided $\alpha=0.1$). Subjects who require dose reduction, or temporary discontinuation but are able to resume treatment will be considered non-withdrawals.

13.2.2. **Randomization:** The randomization scheme will be a ratio of 2:1 for drug versus placebo. Once a participant has signed the consent form and completed the enrollment visit (and baseline bronchoscopy in subjects who participate in the bronchoscopy substudy), the participant will be randomized. Study medication will be distributed by the VUMC investigational pharmacy according to the randomization scheme.

13.3. **Statistical analysis:** For the primary endpoint, the rate-of-discontinuation of study drug due to adverse events will be compared between valganciclovir and placebo subjects by Chi-square. **Secondary analysis:** Frequencies of specific adverse event profiles will be compared between groups by Chi-square. This study is not powered to detect clinically significant changes in pulmonary function or perform multivariate analyses. Exploratory analyses for physiologic and biochemical endpoints will be performed using standard nonparametric statistics or paired tests when appropriate. The rate of change in FVC (cc/year) will be compared between valganciclovir therapy group (treatment group) compared to the standard of care (placebo) group. For other physiologic measurements (6MWD, oxygenation), similar analyses will be performed. For exploratory biomarker studies, paired analyses (Baseline vs. 12 weeks) will be performed comparing subjects randomized to valganciclovir or placebo. All analyses will be performed using STATA 11.0 (StataCorp, College Station, TX) and the programming language R (50).

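### Section 13.3 tests specific adverse events by chi-square with no level, sidedness, event list or descriptive label, and in 20 versus 10 subjects such tests can neither establish nor rule out a named toxicity

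*Combined protocol and SAP*

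**What the plan says.** Section 13.3 names discontinuation of study drug due to adverse events as the primary comparison. Under the label of secondary analysis it then says: "Frequencies of specific adverse event profiles will be compared between groups by Chi-square". It does not say which events will be compared, at what level, one- or two-sided, or whether the results are descriptive. The same paragraph does use the word exploratory, but for the physiologic, biochemical and biomarker analyses.

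Section 4.1.1 gives these comparisons more weight. There, "safety and tolerability will be determined by type, frequency and duration of adverse events (AE) and serious adverse events (SAE"), with valganciclovir set against placebo.

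Only one significance level appears in the document: one-sided 0.10, with 75% power, in section 13.2.1. It belongs to the withdrawal comparison: "Using a 2:1 randomization (valganciclovir:placebo) and enrolling 30 subjects will allow us to detect an increased withdrawal rate". The excess that section cites for valganciclovir is about 25%. Section 6.1 gives the arms as "treatment with pirfenidone plus valganciclovir (20 patients) or pirfenidone plus placebo (10 patients) for 12 weeks".

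Section 12.1 says which toxicities to expect: "The major side effect of valganciclovir is bone marrow suppression causing anemia, leukopenia, or thrombocytopenia". It adds nausea and diarrhea, which makes five named events.

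**The concern.** The hypothesis in section 2 is that adding valganciclovir has an acceptable safety and tolerability profile, so readers will look to the event-level comparisons for the answer. With no level and no descriptive label, two unsupported conclusions are open. A small p-value among several tests could be reported as a demonstrated side effect. A large p-value for marrow suppression could be reported as evidence that it does not occur. Because the level and sidedness are not fixed, the same data could be read either way after the fact.

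**Working it through.** **Inputs.** Arms of 20 and 10 (section 6.1). One-sided 0.10 (section 13.2.1, stated for withdrawal and borrowed here). Five events (section 12.1; the plan gives no list of events to be tested). The documents give no background event rates, so these are assumed and varied from 2% to 50%, equal in both arms.

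**1. The plan's own power figure.** Take 25% versus 0% withdrawal, 20 versus 10 subjects, one-sided 0.10, pooled-variance normal approximation. The pooled rate is 5/30 = 0.1667.
- Standard error under the null: √(0.1667 × 0.8333 × (1/20 + 1/10)) = 0.1443.
- Standard error under the alternative: √(0.25 × 0.75/20) = 0.0968.
- Power = Φ((0.25 − 1.2816 × 0.1443)/0.0968) = Φ(0.67) = 74.9%.

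This reproduces the stated 75% and confirms that the level is one-sided and belongs to withdrawal.

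**2. Nominal false-signal rate.** Five independent tests at 0.10 give 1 − 0.9⁵ = 41.0%. Ten would give 1 − 0.9¹⁰ = 65.1%.

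**3. Exact false-signal rate.** For a common rate r, each outcome (a events of 20, b of 10) has probability Bin(a; 20, r) × Bin(b; 10, r). The uncorrected chi-square statistic is z², where z = (a/20 − b/10)/√(p(1 − p)(1/20 + 1/10)) and p = (a + b)/30. Summing over the rejection region gives the per-test rate q. Five independent events give 1 − (1 − q)⁵. For example, at r = 10%, q = 11.4% and 1 − (1 − 0.1136)⁵ = 45.3%.

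| Background rate | q, one-sided 0.10 | Five events, harm, one-sided 0.10 | Five events, either direction, two-sided 0.05 | Five events, harm only, two-sided 0.05 | Five events, harm, Fisher one-sided 0.10 |
|---|---|---|---|---|---|
| 2% | 0.6% | 2.9% | 5.3% | 0.0% | 0.0% |
| 5% | 4.5% | 20.6% | 14.7% | 0.0% | 0.1% |
| 10% | 11.4% | 45.3% | 17.3% | 0.4% | 2.0% |
| 20% | 11.2% | 44.7% | 17.2% | 4.9% | 14.0% |
| 30% | 10.6% | 42.9% | 21.3% | 8.8% | 22.0% |
| 50% | 12.4% | 48.3% | 23.4% | 12.3% | 21.6% |

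Between these rows, the uncorrected one-sided figure peaks at 48.8% (rate 15%) and Fisher's at 22.6% (rate 35%). A continuity-corrected chi-square gives 0-21%.

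**4. Mixed rates and correlation.** With hematological events at 10% and gastrointestinal events at 30%, the one-sided 0.10 figure is 44%. It falls to about 38% with a latent within-subject correlation of 0.5. With rates of 5% and 20%, it is 31%, falling to about 28%.

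**5. Power for one real toxicity**, by the same enumeration with unequal rates:
- 5% rising to 20%: 50% at one-sided 0.10, 5% at two-sided 0.05.
- 10% rising to 30%: 51% and 16%.

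**6. One data set, two readings.** With 3/20 versus 0/10, p = 0.10 pooled and z = 0.15/√(0.10 × 0.90 × 0.15) = 1.29. The one-sided p-value is 0.098 and the two-sided p-value 0.197. The result is significant at one-sided 0.10 and not at two-sided 0.05.

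**7. Fit of the approximation.** The expected placebo count is 10 × the pooled rate, which is below 5 whenever the pooled rate is below 50%. Uncorrected chi-square and Fisher's test therefore differ widely in step 3.

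**The case against.** The strongest reply is that this is a 30-subject pilot in which no decision turns on these p-values. Under section 14 the stopping rule counts withdrawals, and study personnel review all adverse events and safety laboratory results every two weeks. No passage says that a p-value will establish or exclude a toxicity, and safety comparisons are commonly left unadjusted. This stands, and it limits the matter to how results will be read and reported. It also favors a descriptive label, since no multiplicity adjustment is being asked for.

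Three stronger readings are tempting, and the documents do not support them.
- A reader might infer that the plan has no hierarchy. Section 13.3 does place these tests below the discontinuation comparison. What is missing is any order among the events.
- A reader might take one-sided 0.10 as the level for these tests, and a false-signal rate of 35-45% as a property of the trial. The level is stated for withdrawal only. The rate needs five uncorrected tests and background rates of about 10% or more. Sections 7.2.19.2 and 7.2.25 exclude subjects with low blood counts and certain marrow disorders, so lower hematological rates are plausible.
- A reader might take the 15-23% at two-sided 0.05 as the chance of a false signal of harm. It counts differences in either direction. The harm-only figure is 0-12%.

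**Conclusion.** The concern holds as a gap in wording that bears on the safety conclusion. Section 13.3 specifies a test for each specific event but not the terms on which it would be read, and 20 versus 10 subjects cannot support event-level verdicts in either direction.

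The size depends on assumptions the documents do not settle: the number of events tested, the level, the form of the test, background rates and correlation. For five events at the borrowed one-sided 0.10, the false-harm chance is nominally 41% and about 20-50% over rates of 5-50%. It is much lower for rarer events or with an exact or corrected test. The firmer result is the lack of power. At the alternatives examined it is about one half at the more lenient level and 5-16% at the stricter one, so non-significance is not evidence of safety.

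The difference between sections 4.1.1 and 13.3 over what the primary endpoint is remains a separate issue, which this change does not resolve.

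**What to change.** Replace the sentence on specific adverse events in section 13.3 with wording such as:

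> Frequencies of specific AEs and SAEs are descriptive. For each event, the number and percentage of subjects affected in each arm will be reported, with the valganciclovir minus placebo risk difference and an exact 95% confidence interval. No claim that a specific toxicity is present or absent will rest on a p-value. The one-sided 0.10 level applies to the AE-discontinuation comparison only.

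This puts no multiplicity penalty on safety signals and needs no further subjects, visits or data. The cost is a change of text and the loss of chi-square p-values for individual events.

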14. Safety and Adverse Events Monitoring: Study personnel will meet bi-weekly to review all safety laboratory data collected on each subject and review all adverse events. The study investigators will decide the appropriate steps to be taken to include dose modifications, and further monitoring. [name] will act as an on-site medical monitor who can become un-blinded to study drug if needed in order to adjudicate side effects are detected and whether they may due to valganciclovir. Planned safety analyses will occur after enrollment of 10 and 20 subjects by the medical monitor. If 5 more subjects have withdrawn from the study due to adverse events in the valganciclovir arm compared to placebo at either interim analysis, the study will be terminated.

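### Does the fixed excess of five adverse-event withdrawals at both interim looks make the first safety look too strict to be useful?

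*Combined protocol and SAP*

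**What the plan says.** Section 14 sets the timing: "Planned safety analyses will occur after enrollment of 10 and 20 subjects by the medical monitor". The study is terminated on one criterion, the same count at both looks: "If 5 more subjects have withdrawn from the study due to adverse events in the valganciclovir arm compared to placebo at either interim analysis". The plan gives no chance of firing for either look.

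The trigger has other oversight around it. Section 14 also states: "Study personnel will meet bi-weekly to review all safety laboratory data collected on each subject and review all adverse events". The investigators decide what follows, and the medical monitor may be unblinded to judge side effects. None of this carries a study-level number.

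Four other statements bear on the rule:

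- Section 6.1 allocates subjects to "pirfenidone plus valganciclovir (20 patients) or pirfenidone plus placebo (10 patients) for 12 weeks".
- Section 13.2.2 adds only this on the scheme: "The randomization scheme will be a ratio of 2:1 for drug versus placebo". It gives no block size.
- Section 13.2.1 does not expect any "placebo treated subjects to withdraw from this study", and sizes the trial to detect an "increased withdrawal rate in the valganciclovir group in the range of 25" per cent, with 75% power at one-sided alpha 0.1.
- Section 13.2.1 also says that subjects with dose reduction or "temporary discontinuation but are able to resume treatment will be considered non-withdrawals".

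**The concern.** The second look has about twice as many valganciclovir subjects as the first, yet the count needed to stop is the same. In proportion, the first look is about twice as strict. With no placebo withdrawals, five events at look 1 are still at least five at look 2, so look 1 cannot stop a study that look 2 would let through. Its only value is to stop sooner. If it almost never fires, even when half the treated subjects cannot tolerate the drug, then in a trial whose purpose is safety and tolerability it seems to offer protection that it does not give. At stake are the subjects who start valganciclovir between the 10th and 20th enrolments.

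There is also a difference of wording. Section 14 counts withdrawal from the study, while sections 3.1 and 13.3 count discontinuation of study drug. A subject can stop the drug and stay in follow-up.

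**Working it through.** **Inputs.** Trigger: excess of 5 at either look, looks at 10 and 20 enrolled (section 14). Allocation 2:1, 20 and 10 subjects (6.1, 13.2.2). Placebo withdrawals 0 and a 25% rate on valganciclovir (13.2.1). Treatment for 12 weeks (3.1). Enrolment within 9 months (section 9). Assumed, because the documents do not say: near-exact 2:1 allocation at each look (blocks of 3 in the simulations), even accrual, and the timing of withdrawals.

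**The plan's own figure.** A pooled-variance normal approximation for 25% against 0%, with 20 and 10 subjects and one-sided alpha 0.1, gives 74.9% power. This agrees with the stated 75%.

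**Proportion needed, placebo 0.** Numbers on valganciclovir: 10 × 2/3 ≈ 6-7 and 20 × 2/3 ≈ 13-14.

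- Look 1: 5/7 = 71%, 5/6 = 83%.
- Look 2: 5/14 = 36%, 5/13 = 38%.

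**Chance of firing with complete follow-up.** P(X ≥ 5), X binomial(n, p):

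| True rate p | Look 1, n = 6 / 7 | Look 2, n = 13 / 14 |
|---|---|---|
| 25% | 0.5% / 1.3% | 20.6% / 25.8% |
| 40% | 4.1% / 9.6% | 64.7% / 72.1% |
| 50% | 10.9% / 22.7% | 86.7% / 91.0% |

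The look-1 figures are not bounds. With 8 of the first 10 on drug they are 2.7% at 25% and 36% at 50%.

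**A proportional look 1, for illustration only.** The smallest whole count at look 1 that reaches look 2's proportion is 3 of 6 or 3 of 7. P(X ≥ 3) is then 17% / 24% at p = 25% and 66% / 77% at p = 50%. With complete follow-up and look 2 unchanged, simulation (400,000 runs, blocks of 3) gives a mean number of further valganciclovir starts among enrolments 11-20, at 50%, of 5.4 under the present rule and 1.8 under the illustration. The chance of stopping at either look at a 25% rate rises from 22% to 31%.

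**Whether that saving can be realised.** The looks follow enrolment. Nine months is about 39 weeks, so 39/30 = 1.3 weeks per subject. Waiting 12 weeks for the 10th subject to finish lets 12/1.3 ≈ 9 more enrol, nearly all of enrolments 11-20. Complete follow-up at look 1 and subjects spared afterwards can hold together only if accrual pauses, and the protocol describes no pause.

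**The same comparison with each look on the day of the 10th or 20th enrolment** (1.3-week spacing, blocks of 3, placebo 0%; events spread evenly over the window shown). Each cell gives trigger 5, then trigger 3, at look 1:

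| Withdrawals fall in | Look 1 fires, p = 50% | Mean further valganciclovir starts, p = 50% | Saving, p = 50% | Stop at either look, p = 25% |
|---|---|---|---|---|
| weeks 4-12 | 0%, 6% | 6.67, 6.29 | 0.4 | 5%, 5% |
| weeks 0-12 | 0.4%, 19% | 6.65, 5.38 | 1.3 | 8%, 10% |
| weeks 0-4 | 6%, 54% | 6.28, 3.04 | 3.2 | 16%, 21% |

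At a 25% rate the saving is about 0.05, 0.2 or 0.8 subjects.

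**The case for a change.** The strongest case for a change is that the arithmetic is right and the edit would be short. Look 1 carries the only study-level numerical criterion available that early. The plan gives no reason for using the same count at both looks. At twice the 25% rate, look 1 fires in at most 23% of trials under near 2:1 allocation and complete follow-up, and less often on the enrolment-timed schedule. A sponsor that wanted look 1 to act as a brake would not obtain one from this rule.

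That description stands. What does not follow is that the boundary is wrong. The plan promises neither equal proportions at the looks nor any particular probability of early stopping. The benefit of scaling is large only if withdrawals come in the first four weeks and the true rate is near 40-50%. Section 8.3 interrupts and then reduces study drug for laboratory abnormalities before ending it, and section 13.2.1 does not count resumed interruptions, so withdrawals for laboratory abnormalities would tend to come later, where the gain is smallest. Against the benefit stands more stopping at 25%, the rate that the completed trial is meant to detect. Between looks, the bi-weekly review and the monitor who can be unblinded remain in place, though without a number.

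On the wording, section 13.2.1 uses withdrawal in the sense of stopping treatment for good and says what does not count. A monitor would apply that meaning in section 14. A cross-reference would be tidy, but nothing depends on it.

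**Conclusion.** The observation is correct, but no change to the plan follows. With no placebo withdrawals and allocation near 2:1, look 1 needs 71-83% of valganciclovir subjects withdrawn against 36-38% at look 2. On the schedule in section 14 it would fire about 0-6% of the time at a true 50% rate. It is close to inoperative except under extreme intolerability.

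That is a defensible choice with 6-7 treated subjects. Look 2 keeps the rule's ability to stop the study: 87-91% at a 50% rate with complete follow-up, though less if taken on the day of the 20th enrolment. Scaling look 1 would spare 0.4-3.2 valganciclovir starts on average at 50% and 0.05-0.8 at 25%. The chance of stopping at 25% would move from 5-16% to 5-21%. Which side of that exchange is better is a judgement for the sponsor and the medical monitor. Reporting the firing chances would inform it but would not correct an error.

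The proportions and binomial figures are firm given the allocation and zero placebo withdrawals. The enrolment-timed figures rest on assumed even accrual, blocks of 3 and the event timing shown. Event timing alone moves the saving at 50% about eightfold (3.2/0.4).

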- 8.3. Protocol for dosage adjustment: In subjects who develop a treatment-emergent, nonserious adverse events (i.e. nausea), valganciclovir will be administered in divided doses (450 mg twice daily). In subjects who develop treatment emergent clinically significant laboratory abnormalities possibly related to the study drug, study drug will be held until lab abnormalities have resolved. Current and new medication review will be conducted to assess for alternative contributors to lab abnormalities. After the treatment-emergent laboratory abnormality resolves, subjects will then resume study drug with repeat laboratory monitoring within 1 week after resumption of treatment, or earlier if symptoms recur in an earlier time period. If the treatment emergent laboratory abnormality recurs, study drug will be reduced to 450mg QD with close monitoring. If symptoms or lab abnormalities occur with 450mg QD, the study drug will be terminated.

9. Study Feasibility and Timeline

All subjects will be enrolled through the Vanderbilt Interstitial Lung Disease (ILD) clinics have been top enrolling sites for several multi-center clinical trials in IPF, and given this proven track record, we are confident we will meet enrollment targets. We will place priority on enrollment in this VICTR support pilot trial over industry-sponsored trials. We currently evaluate >200 new IPF cases per year in our clinics. At the present time, approximately 125 IPF patients are being treated with pirfenidone in the Vanderbilt ILD clinic, and the majority of these patients should be eligible for this study. We expect to begin recruiting patients immediately upon approval of this study and complete enrollment within 9 months such that subjects will reach the primary study endpoint by the end of Year 1. Ongoing ascertainment of data collected during routine clinical follow-up of these study subjects will then be completed in Year 2.

10. Study Visits

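### Section 14's two numerical safety looks are timed by enrollment with no exposure requirement, and the event they count should be reconciled with section 13

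*Combined protocol and SAP*

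**What the plan says.** On timing, section 14 states: "Planned safety analyses will occur after enrollment of 10 and 20 subjects by the medical monitor". Termination follows "If 5 more subjects have withdrawn from the study due to adverse events in the valganciclovir arm compared to placebo at either interim analysis". It sets no minimum time on drug and does not say how soon after the 10th or 20th enrollment the look is taken. It gives no stopping probabilities. Section 10.2 allows drug to be mailed once eligibility has been confirmed by telephone, so an enrolled subject may not yet have had a dose.

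On the counted event, section 13.3 says that "the rate-of-discontinuation of study drug due to adverse events will be compared between valganciclovir and placebo subjects by Chi-square". Section 14 instead speaks of withdrawal from the study. Section 13.2.1 uses similar language: it does not expect any "placebo treated subjects to withdraw from this study", and it adds that "Subjects who require dose reduction, or temporary discontinuation but are able to resume treatment will be considered non-withdrawals".

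Other protection is in place. Section 14 also says "Study personnel will meet bi-weekly to review all safety laboratory data collected on each subject and review all adverse events", and it names a medical monitor who can be unblinded. For laboratory abnormalities, section 8.3 goes through hold, resumption and reduction before the last step: "If symptoms or lab abnormalities occur with 450mg QD, the study drug will be terminated".

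**The concern.** Safety and tolerability are the purpose of this trial, and the excess of 5 is its only numerical criterion for ending the study. An enrollment count says nothing about exposure. A subject who enrolled last week can hardly have stopped drug for an adverse event, yet counts toward reaching the look. If the looks come when little drug has been taken, a large excess of discontinuations may not yet show.

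Separately, a subject can stop drug for an adverse event and stay in follow-up, which section 6.1 runs to 12 months. Read literally, section 14 would not count that subject although the primary analysis would.

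**Working it through.** **Inputs.** 30 subjects and 12 weeks of treatment (section 3.1); 2:1 allocation (section 13.2.2); enrollment within 9 months (section 9), about 39 weeks, or one subject per 39/30 = 1.3 weeks if even; no placebo withdrawals, and 25% as the detectable rate (section 13.2.1). The common 13% borrows the pirfenidone discontinuation figure cited there. Assumptions not in the documents: even accrual, blocks of 3, looks at the moment of enrollment, the timing of stops, and the 50% rate.

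**1. The plan's own figure.** The only stated power is 75% for 25% versus 0% at the final analysis, one-sided alpha 0.1. With pooled rate (20 × 0.25 + 10 × 0)/30 = 0.167, the null SE is √(0.167 × 0.833 × (1/20 + 1/10)) = 0.144 and the alternative SE is √(0.25 × 0.75/20) = 0.097. Power = Φ[(0.25 − 1.282 × 0.144)/0.097] = 74.9%. The figure is reproduced; there is no counterpart for the stopping rule.

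**2. Exposure at the looks.** At the 10th enrollment, weeks since entry are 11.7, 10.4, 9.1, 7.8, 6.5, 5.2, 3.9, 2.6, 1.3 and 0. The mean is 5.85; six of ten have reached week 4 and none has finished. At the 20th, the first ten have passed 12 weeks and the other ten repeat this list.

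**3. The threshold with complete follow-up.** P(excess ≥ 5), binomial, placebo 0%:
- Look 1 at 50%: 10.9% (6:4 split) or 22.7% (7:3). At 25%: 0.5% or 1.3%.
- Look 2 at 50%: 86.7% (13:7) or 91.0% (14:6). At 25%: 20.6% or 25.8%.

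So full exposure alone leaves look 1 weak: it needs 5 of 6–7 treated subjects. A strict early count is not in itself a fault. For 5 versus 0, one-sided Fisher p is 6/252 = 0.024 or 21/252 = 0.083 at look 1.

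**4. Staggered entry.** Simulation of at least 200,000 trials per scenario, placebo 0% except in the last two rows. The week 4 looks fall at 9 × 1.3 + 4 = 15.7 and 19 × 1.3 + 4 = 28.7 weeks, when about 13 and 23 subjects are enrolled; all are counted.

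| True rates, trigger | Stops in weeks 4–12 | Spread over 12 weeks | First 4 weeks |
|---|---|---|---|
| 50 vs 0, look 1, enrollment | 0% | 0.4% | 6% |
| 50 vs 0, look 1, week 4 | 1.7% | 7% | 28% |
| 50 vs 0, both looks, enrollment | 48% | 60% | 80% |
| 50 vs 0, both looks, week 4 | 71% | 79% | 91% |
| 25 vs 0, both looks, enrollment | 5% | 8% | 16% |
| 25 vs 0, both looks, week 4 | 11% | 16% | 26% |
| 13 vs 13, both looks, enrollment | 0.2% | 0.3% | 0.7% |
| 13 vs 13, both looks, week 4 | 0.5% | 0.7% | 1.3% |

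With no placebo events the excess cannot shrink, so the overall probability is that of look 2; a better look 1 only brings action forward. For the same reason, adding the week 4 looks to the enrollment looks leaves 71–91% unchanged at 50% versus 0%. At a common 13% it gives 0.5–1.4%.

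**5. Sensitivity** (50% versus 0%, both looks, spread and early patterns, enrollment to week 4 trigger): 6-month accrual 41–76% to 75–93%; 18-month accrual 76–83% to 83–89%; random arrival over 9 months 56–77% to 78–92%. Counting only the first 10 and 20 subjects at the week 4 looks gives 78–88%. Letting early discontinuation bring the look forward leaves 79–91%.

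**6. The counted event.** Section 14 names withdrawal from the study and section 13.3 names discontinuation of study drug. Section 13.2.1 classes a subject who resumes treatment as a non-withdrawal, which implies that withdrawal there means a permanent stop of drug. Section 14 does not say whether it follows that usage.

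**The case against.** The strongest reply is that the trigger is not what makes look 1 weak. That stands: with complete follow-up look 1 reaches only 11–23% at 50%, and after the change it is 1.7–28%. A reader might infer that the enrollment trigger is why look 1 almost never acts; the documents' own threshold of 5 is the larger cause.

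A reader might also infer that section 14 counts a different event from the primary analysis. Section 13.2.1 points the other way, so this is an ambiguity and not a demonstrated mismatch. If only half of those who stop drug also left the study, both looks at 50% would fall from 60–80% to 8–16% (spread and early patterns), but that share is invented and the documents give none.

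The plan does not say the look happens at the instant of enrollment. With a 2-week lag the current rule already gives 71–86% for the spread and early patterns, so part of the gap closes. This stands as a limit on the size of the gain.

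Stops may also come late. Section 12.1 names bone marrow suppression as the major side effect, and the section 8.3 sequence takes time, so a week 4 look may precede many laboratory-driven stops. The weeks 4–12 column covers this: the overall gain remains (48% to 71%), but look 1 barely moves.

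Finally, bi-weekly review, the monitor and section 8.3 operate throughout. It would be wrong to infer that subjects are unprotected between looks. The numerical rule is a backstop.

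**Conclusion.** The point holds in a limited form, as a cheap improvement. Section 14 applies its only numerical trial-level rule without regard to exposure. On the planned 9 months, at 50% versus 0%, look 1 fires about 0–6% and both looks together about 48–80%; a week 4 condition lifts the latter to about 71–91% with little added false stopping. The whole overall gain is at look 2.

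These figures rest on even accrual, blocks of 3, immediate looks, assumed stop times and a 50% rate that the documents do not mention. The gain shrinks with slower accrual or if looks are in practice taken some weeks after enrollment. Sensitivity at 25% stays low under either trigger; that rate is the final-analysis target and not a stated stopping target. The wording of the counted event needs reconciling whatever those assumptions are.

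**What to change.** In section 14:

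1. Add a look when the 10th and again when the 20th subject completes the already scheduled week 4 visit, or discontinues before it, counting all subjects exposed by then. Alternatively, move the existing looks to those points if the sponsor and the medical monitor accept the delay.
2. Reconcile the counted event with section 13 by stating that the rule counts permanent AE-related discontinuation of study drug, reported with the number exposed in each arm.

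A short table of stopping probabilities, with its accrual and allocation assumptions, would help but is optional. Whether to keep the count of 5 is for the sponsor and the medical monitor.

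The cost is protocol wording, with no new visits or data. Adding looks means two more reviews. Moving them makes each look about 4 weeks later, with about 13 and 23 subjects enrolled in place of 10 and 20, while the other safety review continues.
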